### 3.0 Governance

The Statewide Clinical Renal Network (SCReN) has facilitated formation of a steering committee (Governing body)

[figure not shown]
#### Purpose

To establish a registry of patients with biopsy-proven renal disorders, through the collaboration of CKD.QLD (University of Queensland), the SCReN and Renal Physicians from other Hospital and Health Services across Queensland.

#### RELATIONSHIPS

##### *Governance / Reporting Structure:*

- The Qld.Renal Biopsy Registry Steering Committee will report to SCReN through the Chair of the committee.

Steering Committee Members

## 4.0 Introduction

The diseases of the kidney can be broadly classified into acute kidney injury (AKI) and chronic kidney disease (CKD). AKI is abrupt decline in kidney function and CKD is progressive loss in kidney function over a period of months to years. AKI occurs in about 17% of patients admitted to the hospital in Australia and New Zealand. Patients who develop AKI have higher rates of morbidity and mortality, and quarter of them may progress to CKD. The impact of AKI on the health care budget is substantial when compared to the hospital costs to patients without AKI. AKI is mainly due to sepsis, hypovolemia, following major surgery, exposure to nephrotoxins, and is often associated with other organ failure. A renal biopsy is required in AKI of unknown aetiology to obtain information for diagnosis, management and prognosis. In a Spanish study renal biopsy confirmed AKI in children, adults and elderly was 5.7, 12.5% and 32.9% respectively.

CKD pose a significant burden to health care system and in 2012 direct and indirect costs in managing CKD was \$4.1 billion (<http://kidney.org.au/>). Approximately 1 in 10 Australians have indicators of CKD and 10% of patients visiting a general practitioner have CKD (<http://kidney.org.au/>). CKD can progress to end stage renal disease requiring renal replacement therapy (RRT). At the end of 2014 overall prevalence of people receiving RRT in Australia was 947 pmp. Three most common causes of kidney disease requiring long-term RRT were diabetes, glomerulonephritis and hypertension (<http://www.anzdata.org.au/>). Nephrologists have to perform a kidney biopsy to diagnose and prognosticate glomerulonephritis and tubulo-interstitial disorders. In 2014 20% of the patients who started long-term RRT were due to these disorders of the kidney. There is paucity of information on management strategies and therapeutic outcomes of these patients as there is lack of consensus in definitions, recommended treatment modalities, and clinical / research collaboration. The Renal Biopsy Registry will facilitate specific target-guided therapy, “evidenced” rather than empirical therapy. The Registry will help identify potentially mixed pathology, identify population-based or regional patterns, and trends in certain sorts of kidney disease e.g. environmental problems, CKDu, environmental, occupational, and toxic nephropathies etc, and will characterize apparently newish syndromes e.g. proton pump inhibitor -associated nephropathies. In many developed countries renal biopsy registries have been initiated to address these issues but no similar registry exists in Australia. We therefore aim to establish a renal biopsy registry in Queensland and later expand the registry across Australia.

### 4.1 Plain language statement

Each kidney is made of about one million tiny structures called nephrons. Kidneys fail when diseases injure these nephrons. Kidney injury may occur in short term called acute kidney injury (AKI) or kidney function may worsen over months to years known as chronic kidney disease (CKD). People suffering from AKI recover their kidney function with treatment but in some, AKI may lead to CKD. About 14% of Australian adults have CKD with higher rates with age and in indigenous Australians. [[http://kidney.org.au/cms\\_uploads/docs/kha-economic-impact-of-eskd-in-australia-projections-2020.pdf](http://kidney.org.au/cms_uploads/docs/kha-economic-impact-of-eskd-in-australia-projections-2020.pdf)]. Some of these patient’s progress to end stage kidney disease (ESKD). Glomerular and tubular disorders can result in AKI and CKD and as a group is the second leading cause of ESKD in Australia and New Zealand among those who opt for dialysis and transplantation. There is a great variation in outcomes of these disorders. There is some information on the epidemiology, but the variation is still poorly understood.

When the cause of kidney disease is unclear, develop treatment plan and or assess prognosis renal physicians perform a kidney biopsy. The biopsy is sometimes used to define the extent of damage and evaluate how well the treatment is working. And the things usually examined on biopsy are nephrons, the functional unit of the kidney. It is composed of tiny filters known as *glomeruli*, the fluid from these filters

are modified in conduits called *tubules* and in association with *interstitium*, the tissue surrounding and supporting these structures. “Glomerular disorders, Glomerulonephritis and Glomerulopathies” [GN] and tubulointerstitial nephritis refer to a range of kidney conditions which cause inflammation of these structures in the kidney. This occurs due to a problem with the body’s immune system.

The purpose of this study is to establish a state-wide renal biopsy registry to collect detailed clinical information of patients suffering from these disorders. Analysis of the database will provide opportunities for better understanding of the longitudinal course and outcomes of these patients. The data will be used to formulate guidelines for management. There is a long-term plan, pending additional ethical approval, to establishing a nationwide renal biopsy registry.

## 4.2 Background

Kidney injury can be either acute or chronic. The incidence of AKI in hospitalised patients using a KDIGO – guidelines was 16.9% in Australia and New Zealand [1]. Subsequent renal decline was greater after AKI (vs no AKI) (14.8% vs 10.8%); even if post-discharge kidney function returns to normal; overall, 25 percent of AKI patients progress to chronic kidney disease [2]. The first national report on AKI in Australia has shown that AKI is a growing problem and AKI affects living in socioeconomically disadvantaged areas had higher AKI hospitalisation and death rates in the population more than others.

<http://www.aihw.gov.au/WorkArea/DownloadAsset.aspx?id=60129552567>. National renal biopsy registries provide useful information in biopsy confirmed acute kidney injury. Spanish data on renal biopsy study collected over a decade showed 16.1% of the biopsies were diagnosed with acute kidney injury [3]. Studies from this registry showed that the prevalence of biopsy-confirmed acute renal failure according to aetiology was vasculitis, 23.3%; acute tubulointerstitial nephritis, 11.3%; and crescentic glomerulonephritis types 1 and 2, 10.1%. This study also highlighted that the prevalence of the different causes differed significantly according to age group [3].

Approximately 1.7 million Australian adults have chronic kidney disease, and some may progress to end stage kidney disease [www.kidney.org.au]. The most common causes of CKD in Australia are diabetes mellitus, glomerular and tubulointerstitial disorders of the kidney and hypertension. Glomerulonephritides (GN) and tubulointerstitial disorders have an incidence of 0.7 -2.8 per 100,000/year [4] and are the second leading cause in patients with ESKD requiring renal replacement therapy in Australia and New Zealand [ANZDATA] [5]. Annual estimated cost of a hospital haemodialysis patient is about A\$ 80,000. These disorders therefore pose a significant burden to the health care system as the risk of progression to end stage kidney disease (ESKD) is high. Renal biopsy registries have been started in many countries to understand their epidemiology, enhance nephrologists’ collaboration to improve patient care, and evaluate new clinical care [1,6]. There is a dearth of high quality clinical trials due to reasons such as lack of consensus in definitions, low prevalence of disease, difficulty in recruitment, high costs of trials and lack of collaboration. The creation of renal biopsy registry could facilitate to conduct high quality trials [7]. There is no established renal biopsy registry in Australia. Data on epidemiology of biopsy proven GN was first published from Victoria in 2001[8] and fifteen years later from Queensland [9]. There have been no significant changes over time with age, gender or incidence of biopsy proven GN in Australia [9]. A recent study on biopsy proven GN from New Zealand has shown age, hypertension and heavy proteinuria at diagnosis are strong predictors of progression to ESKD and death [10].

Nevertheless, there is a paucity of data on management strategies and therapeutic outcomes of these disorders. There is an increasing incidence of crescentic GN over the last decade and 75% is due to Anti neutrophil antibodies associated GN [ANCA GN] [9]. There is gross variation in biopsy proven ANCA GN across two metropolitan Queensland hospitals though they provide services to a population of about a million each. (Unpublished observations –[name]): Silica dust from mining industry is considered as a risk

factor [11,12]. There is also a suggestion that there is a relation between the effect of severe cyclones and storms on the incidence and clinical phenotype of ANCA associated vasculitis [13]. The exact reasons either for increasing trend or for disparity in different locations are not known. Aboriginal adults have an increased incidence of CKD and kidney failure [14]. It may be explained by low birth weight and infection causing GN in their childhood but not entirely understood [15]. Lupus Nephritis, another form of GN has been shown to be predominantly seen in Australians of Asian descent [16]. Dysregulation of the alternative pathway of complement involving the kidney can result in atypical haemolytic uremic syndrome (aHUS) and C3 glomerulopathy. Alternative pathway may also be involved in other forms of glomerulonephritis such as anti-neutrophil cytoplasmic antibody mediated GN and immunoglobulin A (IgA) nephropathy [17]. Even though there is some information that genetics, geography, environment, race and socio-economic conditions play a role there is not enough data on the longitudinal course, management strategies and therapeutic outcomes of these patients, and there is little clinical and or research collaboration. Australian Institute of Health Welfare reports that there is not enough information on managing glomerulonephritides ([http://kidney.org.au/cms\\_uploads/docs/kha-economic-impact-of-eskd-in-australia-projections-2020.pdf](http://kidney.org.au/cms_uploads/docs/kha-economic-impact-of-eskd-in-australia-projections-2020.pdf)). There are no long –term studies from Australia on the outcome of biopsy proven acute kidney disorders or tubulointerstitial nephritides

A comprehensive database including patient demographics, co-morbidities, laboratory investigations, histological diagnosis, treatment and outcome of biopsy proven renal disorders is therefore required.

Renal transplant histology is variably obtained at surgery after clamp release. Allograft biopsy is more frequently performed when acute or chronic rejection, recurrence of native disease, denovo GN, tubulointerstitial nephritis, calcineurin toxicity, microangiopathy and unexplained renal dysfunction are considered. Some centres perform protocol biopsies as well. Data accrual across the state reflects varying immunosuppression and its effects that contribute toward allograft health and provide valuable information in optimising therapy.

Queensland has a population of about 4.8 million, a mix of socioeconomic status that includes indigenous Australians and peoples that are culturally and linguistically diverse. Queenslanders live in metropolitan cities, smaller towns and rural and remote areas. Queensland is approximately 1/5th of the country by size and has approximately 1/5th of the dialysis population. As a state, Queensland is representative of both the national Australian population in general, and the renal population.

#### **Existing Renal Biopsy/GN Registries:**

Several renal biopsy exist to address the natural history of medical renal disease, describe their clinical features, evaluate treatment, understand risk factors for complications, support studies and health services research in these disorders.

- ***Danish Renal Biopsy Register (1985)***

Renal biopsy registry was established in the kingdom of Denmark in 1985 with the aim of accumulating comprehensive clinical and pathologic information related to all renal biopsies done in Denmark.

- ***The Toronto Glomerulonephritis Registry [1986]***

[<https://www.symptoma.com/en/research/profile/toronto-glomerulonephritis-registry-group>]

A regional program for studying the natural history of the different types of glomerulonephritis and the effects of drug therapy on them was established in Toronto. Data for all patients with histologic evidence of glomerulonephritis seen at the participating hospitals are collected on standard forms

and stored in a computer. Randomized controlled trials of different types of therapy for glomerulonephritis are conducted under the coordination of the central registry.

- ***The Czech registry of renal biopsies (1993):***  
Renal Biopsy registry was established in Czech Republic '. Aims of this registry are to study the epidemiology of renal disorders based on histologic diagnosis and to identify the most frequent clinical syndromes [15]
- ***Spanish registry of Glomerulonephritis [1994]*** [<http://www.nephropathology-esp.org>] studies the epidemiology of renal diseases in Spain was established to know the prevalence and incidence of biopsied renal diseases and study the relationship between clinical data and histologic patterns.
- ***Italian nephrologists [1996]*** collect the data relating to renal biopsies in a national registry, Italian Registry of Renal Biopsies [<http://www.irrb.net>] to conduct epidemiologic studies in health care to answer the several open questions in both prevention and treatment of renal diseases.
- ***Japanese Society of Nephrology [2007]*** started the first nationwide, web-based, and prospective registry system, the Japan Renal Biopsy Registry [J-RBR], to record the pathological, clinical, and laboratory data of renal biopsies [18].
- ***The British Columbia GN Network and Registry [2013]*** [6] is a unique model in that it combines robust data capture, data linkages, and health care delivery and evaluation into one integrated system. This registry includes all patients in provincial renal database who had a renal biopsy, irrespective of diagnoses. They collect extensive data to study the risk of progression to ESKD and healthcare resource utilization. This registry comprises of both these elements capturing data prospectively utilising the existing health infrastructure.

## 5.0 Study Aim and Objectives

To establish a registry of patients with biopsy-proven renal disorders enabled by a collaboration of the State Wide Clinical Renal Network [SCReN], Renal Physicians from Hospital and Health Services across Pathology Queensland and CKD.QLD [The University of Queensland].

The principal aim of the Registry is to improve patient care and outcomes. The Registry will do this by profiling renal biopsy proven disorders in Queensland which will facilitate early recognition, benchmark management to best practice, and provide a platform to validate new care strategies.

Specific objectives include:

- Development of a prospective collection of clinical, laboratory, pathology, treatment and outcome data of patients with biopsy proven medical renal disease
- Consolidation of data into a collated data set [Registry]
- Evaluation of patient data to identify and facilitate improved clinical care and management
- Support clinical research
- Identification and development of health policies targeting patients with biopsy proven renal disorders
- Develop links and collaborations with other registries nationally and internationally

## 5.1 Hypothesis:

A Renal Biopsy Registry will facilitate research and provide a single access point of data for treating clinicians, patients and their families, supporting improved patient care, management and research, with an understanding for health economics and supporting improved health service delivery in the future.

No comprehensive information on role of geography, environment, race and socioeconomic conditions causing these disorders. There is not enough data on incidence, prevalence, longitudinal course, management strategies and therapeutic outcomes of these patients, and, there is little clinical and or research/ collaboration. To address this problem developed countries have established registries. The plan is to establish a Queensland renal biopsy registry. The long-term objective is to expand to a national renal biopsy registry once the Qld registry is established both in feasibility, governance and first outcomes. This is an observational study.

## 6.0 Study Method

### 6.1 Study Design

#### **Definition of biopsy proven renal disorders for purpose of the registry:**

Data of the patients who underwent histopathological examination of their renal tissue will be collected in this registry. Malignancy related renal biopsies will be excluded from this registry

#### **Glomerulonephritides / Glomerulopathy:**

**Proliferative glomerulonephritis** is characterised by increased glomerular cellularity with the proliferation of indigenous cells and/or leucocyte infiltration; the main categories of proliferative glomerulonephritis are immune-complex proliferative GN, pauci-immune GN, anti-Glomerular basement membrane (GBM) GN, proliferative monoclonal immunoglobulin GN, and C3 GN. Other non-proliferative glomerulopathies include the presence of immune complex deposition without cellular proliferation (in membranous nephropathy), podocytopathies (minimal change disease and focal segmental glomerulosclerosis-FSGS), the deposition of amyloid or monoclonal immunoglobulin deposits, and glomerular changes secondary to diabetes mellitus, in the absence of any of the conditions described above.

#### **Tubulointerstitial disorders**

Tubulointerstitial kidney diseases are those in which the tubules and interstitium, rather than the glomeruli, are the primary sites of injury. These conditions include acute tubular injury from ischaemia or toxins, as well as tubulointerstitial nephritis due to viral infections, drug reactions and hereditary conditions. Some systemic diseases may also cause tubulointerstitial kidney disease, such as the cast nephropathy associated with multiple myeloma, and interstitial nephritis associated with autoimmune conditions such as systemic lupus erythematosus

#### **Phase 1A: Retrospective Data**

##### **Retrospective analysis of data collected for the study on epidemiology of Biopsy proven Glomerulonephritis in Queensland - LR 10/48**

This retrospective analysis reviewed the data from all adult native renal biopsies performed in the state of Queensland from 2002 to 2011--comparing results with centres from across the world. Pathology reports of 3697 adult native kidney biopsies were reviewed, of which 2,048 had GN diagnoses. Age, gender, clinical indication and histopathology findings were compared. Further

analysis of this data will provide information on treatments administered and outcome of the patients with glomerular disorders.

### **Retrospective analysis of Data**

Data of all the patients who underwent renal biopsy from 2002-2018 will be collected. This includes the data collected for the study on “Biopsy proven Glomerulonephritis in Queensland - LR 10/48”.

### **Phase 1B: CKD.QLD patient data linkage - prevalent patient data.**

At time of writing, 9,005 patients have consented to the CKD.QLD Registry via informed consent. Approximately 13% (1,000) of these patients have had a renal biopsy as part of their routine clinical care and diagnosis of their renal disease process. These patients will facilitate a platform of prevalent patient data, with outcomes, for the establishment of the Renal Biopsy Registry.

**Note:** CKD.QLD has an established collaborative framework with state data custodians including the Health Service Information Agency (HISA) and Pathology Queensland, in addition to all HSS Renal Services as founding Registry members (providing a logistic framework for chart audits if needed).

### **Phase 2: Collection of data prospectively.**

Data of all incident consenting patients with biopsy proven renal disorders referred to the above public hospitals will be collected. Of note: an average of 300 renal biopsies are performed annually in the public [government funded] sector, each of which is stored in a single Queensland Health laboratory system. The data of incident patients with diagnosed biopsy-proven renal diseases from Queensland public health and selected private renal services will be collected.

## 6.2 Study Settings

### 6.2.1 Sample size

The study is an observational study on different subset of renal biopsy proven disorders and therefore no power calculations can be made. We estimate there are about 200 patients with biopsy proven glomerulo-tubulointerstitial disorders are seen annually in public hospitals.

### 6.2.2 Data to be collected

#### ***No blood or tissue samples will be collected or stored***

- Patient demographic data including gender, age, weight at birth, ethnicity, postcode, current and past occupations.
- Co-morbidities, date of diagnosis, clinical features, pathology including serial renal function tests, immunological tests, imaging results, and renal biopsy.
- Renal management: Medications, plasmapheresis and dialysis if performed, time from referral to date of renal biopsy, time from referral to initiation of treatment.
- Referral patterns: renal function at referral to renal service and referral history.
- Patient outcomes: disease progression, commencement of renal replacement therapy,
- Death

### 6.2.3 Data analysis

Descriptive statistics and frequency distributions will be done for continuous and categorical variables respectively. The association between renal function and risk factors [e.g. age, sex, time

taken for referral, renal function on presentation, will be calculated and analysed by bi-variate [unadjusted] and multivariate analysis [adjusted].

All analyses will be undertaken using Stata 13.1 [Stata Corp. Stata Statistical Software: Release 13.1 College Station, Texas].

Regional mapping of biopsy proven renal cases across Queensland will be done using ARCGIS [Aeronautical Reconnaissance Geographic Information System ARCIS] to identify possible regional clustering which could give hints on aetiology, including possible exposures.

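### The search for regional clustering starts from a map of cases, with no population denominator and no handling of regional differences in biopsy practice or coverage

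*Protocol*

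**What the plan says.** The last paragraph of Protocol section 6.2.3 (Data analysis) contains the whole spatial plan. "Regional mapping of biopsy proven renal cases across Queensland will be done using ARCGIS", and the purpose is "to identify possible regional clustering which could give hints on aetiology, including possible exposures". The section names the mapped quantity (cases), the software and the inference. It names no population at risk, no standardisation, and no treatment of differences between regions in who is biopsied or who enters the registry.

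Other sections bear on this:

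- **Population.** Section 4.2 (Background) states "Queensland has a population of about 4.8 million" and "Queenslanders live in metropolitan cities, smaller towns and rural and remote areas".
- **Case numbers.** Section 6.1, Phase 2, states that "an average of 300 renal biopsies are performed annually in the public" sector. Section 6.3.1 estimates 300 patients a year. Section 6.2.1 has a lower figure: "We estimate there are about 200 patients with biopsy proven glomerulo-tubulointerstitial disorders are seen annually in public hospitals".
- **Entry to the registry.** Section 6.3 requires a biopsy result and, for incident patients, consent. It excludes people who do not understand English when no interpreter is available. Phase 2 covers the public services and only some private ones.
- **Data items.** Section 6.2.2 collects age, gender, ethnicity and postcode.

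**The concern.** A count of cases in a region is the product of three things: how many people live there, how often they have the disease, and how likely a person with the disease is to be biopsied and enrolled. Only the second bears on cause. In a state settled as unevenly as section 4.2 describes, the first will dominate a count map, and the third can vary with local nephrology practice, private care and consent.

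The Background shows why the third component matters. It reports that "There is gross variation in biopsy proven ANCA GN across two metropolitan Queensland hospitals". By the same account, each of the two serves roughly one million people. With catchments of similar size, population does not explain the contrast, but a map of cases cannot tell a difference in disease from a difference in referral or biopsy threshold.

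Regional patterns and environmental or occupational causes are among the stated reasons for the registry (sections 4.0, 4.2 and 5.1), and section 6.6 commits to reports at least annually. A map read as planned could draw attention to populous or readily biopsying areas and pass over a real excess in a small or remote one.

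**Working it through.** The protocol gives no numerical result for the mapping, so there is no figure to reproduce. The check asks what a case map would show under its own numbers.

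**Inputs from the protocol**

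- State population: 4.8 million (section 4.2).
- Cases per year: 200 (section 6.2.1) or 300 (section 6.1, Phase 2, and section 6.3.1). Both are carried through.
- Large catchment: 1 million (section 4.2, the two metropolitan hospitals).

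**Assumed inputs**

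- Small region: 50,000 people.
- True excess in the small region: rate ratio 2.
- Ratio of biopsy readiness between units at equal disease risk: 1.25 to 2.

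**Step 1. Uniform rate** = cases per year / population.

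- 200 / 4,800,000 = 4.17 per 100,000 per year.
- 300 / 4,800,000 = 6.25 per 100,000 per year.

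**Step 2. Counts at equal risk** = rate × regional population.

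| Cases per year, state | 1 million | 50,000 | 50,000, rate doubled |
|---|---|---|---|
| 200 | 41.7 | 2.1 | 4.2 |
| 300 | 62.5 | 3.1 | 6.25 |

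At equal risk the counts differ by 1,000,000 / 50,000 = 20-fold. With the small region's rate doubled, its count is still 2 / 20 = one tenth of the large region's. Its rate would have to be 20 times as high for the two counts to match.

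**Step 3. Does more data help?** Phase 1A adds biopsies from 2002 to 2018, which is 17 years. At 300 a year, the 1 million catchment accumulates 17 × 62.5 = 1,062.5 cases and the 50,000 region 17 × 3.125 = 53.1. The ratio is still 20. More years reduce chance variation but do not supply the denominator.

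**Step 4. The same regions on a rate scale** (300 a year). At equal risk both show 6.25 per 100,000. With the rate doubled, the small region shows 6.25 / 50,000 = 12.5 per 100,000, a ratio of 2. At 200 a year the figures are 4.17 and 8.3. The excess that the count map hides becomes visible.

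**Step 5. What a population denominator leaves behind.** In a catchment of 1 million, 62.5 cases a year are expected. If its unit biopsies 1.25 to 2 times as readily at the same disease risk, 62.5 × 1.25 = 78 to 62.5 × 2 = 125 are observed. The standardised ratio is then 1.25 to 2 with no difference in disease. Standardisation removes the settlement pattern but not biopsy practice.

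**The case against.** The strongest reply is that one sentence naming software and purpose is not a full method, and that denominators, smoothing and cluster tests are commonly left to an analysis plan, which is not at hand here. The authors also think in rates elsewhere: section 4.2 quotes an incidence per 100,000 per year and sets the two hospitals against their catchments. Section 6.2.2 collects the case-level data that standardisation needs. The aim is modest, since the protocol speaks only of hints from possible clustering.

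Much of this stands, and it rules out three stronger readings:

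- **That the protocol has chosen counts over rates.** A reader might infer this, but section 6.2.3 does not exclude rates, and an analysis plan could add them.
- **That the map can say nothing about cause.** This is too absolute. An extreme local excess, or one confined to a single diagnosis, could still suggest a hypothesis, and the protocol claims no more.
- **That small-area counts will be near zero and a predictable share of hot spots false.** The protocol speaks of regions and fixes no area size. Any such share would depend on assumed areas and on whether the retrospective biopsies are included. For 2002 to 2011 alone these number 3,697 adult native biopsies, of which 2,048 had a glomerulonephritis diagnosis (section 6.1, Phase 1A).

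The reply does not remove the main point. The sentence does more than leave a detail open: it fixes the quantity mapped and the inference drawn, and the first does not serve the second. Nothing in the protocol obliges a later plan to correct this.

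**Conclusion.** The concern holds in a limited form. As written, the mapping ties case location to possible cause without a denominator and without dealing with biopsy practice, consent or private-sector coverage. A map that followed the wording would mainly reflect where people live and who is ascertained. By the protocol's own case and population figures, equal risk produces a 20-fold difference in counts between a catchment of 1 million and a region of 50,000, and a doubled rate in the latter stays at one tenth of the former's count.

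The case total, state population and catchment size come from the protocol. The region of 50,000, the rate ratio of 2 and the biopsy ratios of 1.25 to 2 are assumptions. The rates are crude, set public-sector numbers against the whole state population, and treat one biopsy as one case. The direction does not depend on these choices; the size does.

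This should be fixed, but it is not critical. The analysis is exploratory, the case-level data are already planned, and denominators can be added at the analysis stage.

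**What to change.** Replace the mapping sentence in section 6.2.3 with wording such as:

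> For each region of residence at the time of biopsy, observed cases will be compared with the number expected from census population by age, sex and Indigenous status, using areas large enough to give adequate expected counts. The same map will be produced for all native biopsies, and each diagnosis will also be shown as a share of total biopsies. Regional differences in biopsy practice, consent and private-sector coverage will be considered in interpretation, and any excess will be reported as hypothesis-generating.

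The second sentence is needed because of Step 5: a region with a high standardised ratio for every diagnosis points towards biopsy practice or coverage, whereas a raised share of one diagnosis is harder to explain that way. The choice of smoothing method and cluster test can be left to the analysis plan.

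The cost is a change of wording and the use of census denominators. Age, gender, ethnicity and postcode are already collected; postcode should be recorded as at the date of biopsy. The price is coarser areas and fewer apparent hot spots.
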